INDONESIA UNIVERSITY

THE EFFECT OF TETRAGONULA AFF TOLERANT PROPOLIS
ETHANOL EXTRACT. BUREAU OF ENDOMETRIOSIS LESI
GROWTH, APOPTOSIS ACTIVITY CHANGE AND NETWORK
ENDOMETRIOSIS ACTIVITIES

[figure not shown]
STUDY PROTOCOL

[name]

FACULTY OF MEDICINE
MEDICAL SCIENCE DOCTORAL PROGRAM

JAKARTA
AGUSTUS 2019

STUDY PLANNING

[figure not shown]
The study involved 80 endometriosis mice which were randomly divided into 16 distinct groups: the sham (SH) -0, SH-2, SH-4, SH-6, negative control (KN) -2, KN-4, KN groups -6, positive control (KP) -2, KP-4, KP-6, Dosage of Propolis 1 (P50) -2, P50-4, P50-6, Dosage Propolis 2 (P100) -2, P100-4, P100-6. All mice that will be made endometriosis models are certain to have a normal estrous cycle. The first laparotomy was performed to make an endometriosis model according to the Vivian technique, which was confirmed to be successful 30 days later with a second laparotomy. Subsequently given different treatment according to the study group and carried out a third laparotomy at the appropriate time (2, 4, and 6 weeks after the second laparotomy).

TREATMENT OF RAT

All rats were treated in the ARF IMERI FKUI laboratory. Standard care in research rate follows standard maintenance protocols according to Bauman¹³⁵ to provide optimal well-being for these rats, including: the need for social contact, a place to rest, a place to hide, exploration needs, the need for nutrition and free from environmental disturbances (e.g temperature, sound, etc.)

ESTRUS CYCLE EXAMINATION

The estrous cycle of rats was examined by taking vaginal lavage. Each rat in one cage was marked to distinguish the first to fifth mice. Vaginal discharge is taken by inserting the tip of a plastic pipette containing 10 μ L NaCl 0.9% into the rat's vagina, but not too deep. If the rat is considered aggressive, sampling can be carried out. The vaginal discharge is then placed on a glass slide. Glass slide that is used is different for each cage.

[figure not shown]

PROPOLIS ETANOL EXCRETION

Ethanol Propolis extract (EEP) is made from fine Propolis extracted with 96% ethanol using the method described in Pratami. EEP powder according to the treatment dose was dissolved in 10 cc of aqua before it was given to rat endometriosis models

1st LAPAROTOMY

[figure not shown]
1. Anaesthesia of rats (pentobarbital sodium, 50 mg / kg BW i.m.)
2. Perform Asepsis and antisepsis procedures in the abdomen of the rat

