3. Incision mediana below the center along the 4 cm
4. Treat bleeding
5. Identification of bikornu uterus
6. Resection of rat uterus by 0.5 x 0.5 cm with regard to the endometrium and serous sides
7. Suturing the rat's uterus in the right anterior peritoneum 3 cm from the line
8. incision with the endometrial side facing the peritoneum
9. After there was no bleeding, the abdominal wall was covered in one layer with PGA thread number 2.0
10. Rat returned to the cage, then complete the research form

Bikornu Uterus Identification

Incision in the uterus

Stitching the uterus into peritoneum

2nd LAPAROTOMY

1. Anesthesia of rats
2. Perform Asepsis and antiseptic procedures in the abdomen of the rat
3. The median incision is below the center 4 cm long
4. Treat bleeding
5. After the peritoneum is opened, display the endometriosis lesions that have formed
6. Do lesion documentation
7. Excision of the formed lesion, then insert the tissue into the anatomic pathology tube
8. Cover the entire abdomen using a thread and complete the research form

THE TREATMENT

The treatment is given by sonde orally

PROPOLIS

Each milliliters contains 20mg of propolis. The propolis dosage that we use is 50mg/kg BW. So, we give 0,2ml for propolis 50 treatment, and 0,4ml for propolis 100 treatment

DIENOGEST

We use 0,1mg/Kg BW/day dienogest

WATER

We give 0,2 ml every day for each rat

SPECIMEN COLLECTION

After the treatment is done (for 2, 4, and 6 weeks), we do the necropsy. We take a picture of the lesion (to compare with the beginning lesion), then we take the lesion and peritoneal rinses and blood for the protein level examinations. We also take the ovarium, uterus and peritoneum for pathologic anatomy examination for each treatment.

SPECIMEN EXAMINATION

Protein Levels of Bax, Bcl, Cleaved Caspase 3, IL-1B, and PGE 2

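### Propolis dose and gavage volume double together from P50 to P100, and no volume-matched comparator for P100 is described

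*Combined protocol and SAP*

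**What the plan says.** All treatment is by oral gavage (section THE TREATMENT: "The treatment is given by sonde orally"). Under PROPOLIS in that section, a single strength is stated, "Each milliliters contains 20mg of propolis", with a weight-based dose, "The propolis dosage that we use is 50mg/kg BW", and then two fixed volumes: "So, we give 0,2ml for propolis 50 treatment, and 0,4ml for propolis 100 treatment". Under WATER: "We give 0,2 ml every day for each rat". Under DIENOGEST only a weight-based dose appears, "We use 0,1mg/Kg BW/day dienogest", with no volume.

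The earlier section on preparing the propolis ethanol extract (EEP) describes it differently: "EEP powder according to the treatment dose was dissolved in 10 cc of aqua before it was given to rat endometriosis models". This names water as the vehicle. It also suggests that the concentration varies with the dose.

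STUDY PLANNING lists 16 groups: sham at four times, and negative control, positive control, P50 and P100 at 2, 4 and 6 weeks each. The text does not say which group receives the water. DATA ANALYSIS compares dose and duration groups by ANOVA or Kruskal-Wallis and includes no term for volume. The documents describe neither volume matching nor blinding.

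**The concern.** A vehicle control isolates the active substance only if it receives the same vehicle in the same amount. Here the amount of vehicle rises with the dose. A difference between P100 and P50, or between P100 and the water animals, could reflect more propolis, more fluid by gavage, or both. The comparison of doses is one of the stated aims of the analysis, so the interpretation of the higher dose is at stake.

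A secondary point concerns dosing. A syringe filled to 0.4 mL differs visibly from one filled to 0.2 mL, so whoever doses the animals can tell P100 from P50 and from water.

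**Working it through.** **Inputs.** From THE TREATMENT: concentration 20 mg/mL; volumes 0.2 mL (P50), 0.4 mL (P100) and 0.2 mL (water); P50 dose 50 mg/kg. The P100 dose is read as 100 mg/kg from the group name. From STUDY PLANNING: 80 animals in 16 groups, so 80/16 = 5 per group if the groups are equal.

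**1. The plan's own volumes.** At one concentration, volume = dose × body weight / concentration, so the volume ratio should equal the dose ratio. Dose: 100/50 = 2. Volume: 0.4/0.2 = 2. The 1:2 ratio reproduces. The absolute volumes cannot be reproduced, because no body weight is given (step 5).

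**2. Volume ratios, if water goes only to the control animals.**
- P50/water = 0.2/0.2 = 1 (matched)
- P100/water = 0.4/0.2 = 2 (not matched)
- P100/P50 = 0.4/0.2 = 2, identical to the dose ratio

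P100 versus P50 is a two-group comparison in which two things change together, so dose and volume are fully aliased. Adding the water animals gives doses 0, 50, 100 and volumes 0.2, 0.2, 0.4, with a correlation of 0.87. Three group means could then separate the two effects only by assuming a straight-line dose response, and nothing would be left to check that assumption.

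**3. Volume ratios, if every animal also receives the 0.2 mL of water.** The WATER sentence can be read literally in this way.
- Water only: 0.2 mL
- P50: 0.2 + 0.2 = 0.4 mL
- P100: 0.4 + 0.2 = 0.6 mL

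Volume is then exactly 0.2 + 0.004 × dose: 0.2 + 0.004 × 50 = 0.4 and 0.2 + 0.004 × 100 = 0.6. The match between P50 and water is lost, and the confounding remains.

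**4. Extent.** Three groups receive the P100 volume (15 animals if groups are equal). The same-time contrasts shown to differ in volume are P100 versus P50 and P100 versus water, each at three durations: 2 × 3 = 6. On the reading in step 2, with daily dosing (stated for water, assumed for propolis), the cumulative volumes are:

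| Duration | P100 | P50 or water |
|---|---|---|
| 2 weeks | 14 × 0.4 = 5.6 mL | 14 × 0.2 = 2.8 mL |
| 6 weeks | 42 × 0.4 = 16.8 mL | 42 × 0.2 = 8.4 mL |

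**5. Volume against the weight-based dose.** Amount given = concentration × volume: 20 × 0.2 = 4 mg and 20 × 0.4 = 8 mg. Implied body weight = amount/dose: 4/50 = 0.08 kg and 8/100 = 0.08 kg, that is 80 g in both arms. The documents give no weight. If animals weighed 150 to 300 g (an assumption, to show the range), the stated volumes would deliver 4/0.150 = 26.7 down to 4/0.300 = 13.3 mg/kg in P50, and 8/0.150 = 53.3 down to 8/0.300 = 26.7 mg/kg in P100.

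**6. The two descriptions of the preparation.** An amount of powder set by the dose in 10 cc would allow different concentrations in one common volume. A single 20 mg/mL with two volumes does not. Both cannot describe the same procedure unless more is said.

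**The case against.** The strongest case against is materiality. The unmatched element is 0.2 mL a day of aqueous vehicle, by the same route. Nothing in the documents suggests that this would affect lesion area, Bax/Bcl-2, caspase-3, IL-1B or PGE2. This stands, and it is why the point is graded as a cheap improvement. It does not remove the aliasing.

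Two stronger readings are tempting, and the documents support neither.

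- *A reader might infer that every comparison involving P100 is compromised.* That goes too far. The P100 groups at 2, 4 and 6 weeks share one daily volume, so contrasts between durations within P100 are not confounded in this way. P100 versus dienogest cannot be judged without a dienogest volume.
- *A reader might infer that the volume breaks the blind or uniquely identifies P100.* No blinding is claimed, so no stated mask is broken. With the dienogest volume unknown, 0.4 mL is not shown to be unique to P100. Nothing shows that those who photograph lesions or read the assays would see the volume. Equal volumes would not blind anyone by themselves, and the absence of blinding is a separate matter.

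It can also be said that the water is never assigned to a named group and that the preparation section may intend dose-specific concentrations. Both are fair. The first does not affect P100 versus P50. The second means that the text contradicts itself and must be reconciled, because the treatment section as written gives one strength and two volumes.

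**Conclusion.** The point holds within limits. As written, P100 differs from P50 in dose and in vehicle volume, and from the water animals in propolis and in volume, on either reading of who receives the water. The planned ANOVA or Kruskal-Wallis test cannot undo this. The excess is 0.2 mL a day over P50. Over water it is 0.2 mL a day if water goes only to the control animals, or 0.4 mL a day (0.6 − 0.2) if every animal receives it. The effect on the outcomes cannot be estimated from the documents and is probably small.

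The conclusion assumes that the stated volumes are those actually given. Calling the comparison with the water animals a control comparison further assumes that they are the negative control.

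**What to change.** State one common total daily gavage volume for all gavaged arms, including dienogest, and sham if those animals are gavaged. Reach it either by adding water to the lower-volume arms or by preparing the propolis at dose-specific concentrations, with the intended dose in each arm unchanged. The sponsor chooses the volume. Say explicitly which groups receive water, and whether any animal receives it in addition to another treatment.

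Three items must be reconciled in the same edit: the preparation section (powder by dose in 10 cc) with the treatment section (a single 20 mg/mL in two volumes); the fixed volumes with the weight-based doses, which agree only at 80 g; and the missing body weight. Which figures are correct is for the sponsor to establish.

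The cost is a short protocol edit, plus slightly more fluid in some arms or one more solution to prepare. If dosing is already complete, report the volumes actually given in each arm and describe P100 versus P50, and P100 versus water, as differences in dose and volume together.

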2x QuantiTect SYBR Green PCR Master Mix	7,5 μ L
Primer forward	0,45 μ L
Primer reverse	0,45 μ L
Template cDNA	2 μ L
Total Volume	15 μ L

The reaction mix is then put into a 0.2 ml tube and homogenized by spin down for a few seconds then put into the Techne Prime Pro 48 [Techne] PCR machine and set according to the following table:

Real-time PCR cycle

Steps	Time	Temperature
PCR initial activation step	15 menit	95°C
Denaturasi	15 detik	95°C
Annealing	30 detik	57°C
Ekstensi	30 detik	72°C
Jumlah siklus	40	

The results are then compared with standard curves and analyzed

DATA ANALYSIS

Data on lesion area of endometriosis tissue models, Bax / Bcl-2, Caspase 3, IL-1B, and PGE2 ratios obtained from In Vivo research are numerical data that will be processed using SPSS 20. The data will be presented in the average form if normal distribution or median if not normally distributed. The normality of distribution will be known through the Shapiro Wilk Test. Differences in endometriosis responses between dose and duration groups were performed with the Anova test (normal distribution) or Kruskal Wallis (abnormal distribution). Changes in estrous cycles between groups are known through the chi square test.

To find out the binding of EEP active compounds, it was carried out using the in silico test. Compounds are said to bind when the value of ΔG is less than zero or negative. From the binding compounds, path analysis will be carried out to determine the relationship of the bonds with receptors related to the pathophysiology of endometriosis.

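### One loosely specified Shapiro-Wilk result picks both the summary and the test for each outcome, and neither branch specifies a dose-by-duration analysis

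*Combined protocol and SAP*

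**What the plan says.** The Study Planning section describes the layout: "The study involved 80 endometriosis mice which were randomly divided into 16 distinct groups". The labels give five arms (SH, KN, KP, P50, P100) at 2, 4 and 6 weeks, plus a sham group at time 0 (SH-0). The number per group is not stated. The remark under Estrus Cycle Examination, "Each rat in one cage was marked to distinguish the first to fifth mice", fits five per cage but does not settle group size.

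The Data Analysis section lists the numerical outcomes: "Data on lesion area of endometriosis tissue models, Bax / Bcl-2, Caspase 3, IL-1B, and PGE2 ratios". It names the check: "The normality of distribution will be known through the Shapiro Wilk Test". Normality then controls two choices for each of them:

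- the summary: "The data will be presented in the average form if normal distribution or median if not normally distributed";
- the test: dose and duration groups are compared "with the Anova test (normal distribution) or Kruskal Wallis (abnormal distribution").

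The section does not say whether Shapiro-Wilk is applied to each group, to the pooled raw values or to model residuals. It gives no significance level and no rule for the case where some groups pass and others fail. It does not say whether the ANOVA is one-way or two-way, and it names no interaction term or contrast.

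**The concern.** A data-driven gate is only as good as the test behind it. With about five animals in a group, a normality test can hardly see real skewness. Applied to many groups, it will often reject somewhere by chance. One outcome could then be reported as means with ANOVA and the next as medians with Kruskal-Wallis, although nothing real distinguishes their distributions. Readers could not compare effects across outcomes, and the choice would be made after the data are seen.

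The design also crosses treatment with duration, and the stated question concerns both. Kruskal-Wallis is a one-factor test: it has no separate terms for dose, duration or their interaction. The plan does not commit the ANOVA branch to having them either. So the comparison for which the design was built is not fixed in advance on either branch.

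**Working it through.** The plan gives no significance level, power, SD or effect size, so it has no figure of its own to reproduce.

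**Inputs from the plan**
- Group size: 80/16 = 5, if groups are equal.
- Layout: 5 arms × 3 durations = 15 cells, plus SH-0 = 16 groups. Without the four sham groups, 16 − 4 = 12.
- Numerical outcomes through the gate: 5.

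**Assumptions not in the plan:** gate level 0.05; distribution shapes; independence of outcomes; effect sizes in the examples.

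**1. Gate run by group, any failing group triggers the rank test, data truly normal**
- 12 groups: 1 − 0.95^12 = 0.46.
- 16 groups: 1 − 0.95^16 = 0.56 (simulated: 0.56).

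**2. How often one group of five is flagged (simulation)**
- Normal 5%; lognormal with log-SD 0.5, 10%; exponential 16%; lognormal with log-SD 1, 24%.

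**3. Chance that five independent normal outcomes do not all get the same test: 1 − p^5 − (1 − p)^5**
- By group, 12 groups: 1 − 0.46^5 − 0.54^5 = 0.93.
- By group, 16 groups: 1 − 0.56^5 − 0.44^5 = 0.93.
- One test on 80 pooled residuals, p = 0.043: 1 − 0.043^5 − 0.957^5 = 0.20.

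**4. Other units the gate could use (simulation, 80 animals)**
- Pooled residuals: flagged 4% of the time for normal data, 82% for lognormal with log-SD 0.5, and 99.8% for log-SD 1.
- Pooled raw values with normal errors: 5% with no group differences, rising to 59% when half the groups shift by 3 SD. On this reading a large treatment effect can itself trigger the rank test.

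**5. Can either test address dose by duration?** Rejection rates on the 5 × 3 layout with five per cell, under assumed effects:

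| Test | Additive pattern | Interaction pattern |
|---|---|---|
| Kruskal-Wallis, 15 cells | 76% | 71% |
| One-way ANOVA, 15 cells | 84% | 82% |
| Two-way interaction F | 4% | 30% |

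Neither omnibus test separates the two patterns. Only the interaction term does, and with modest power.

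**6. What the gate costs in power.** Assumed example: 4 arms × 3 durations, five per cell, lognormal with log-SD 0.5, log effects 0, −0.5, −0.25 and −0.5 for the four arms at every duration (3,000 runs):

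| Analysis | Power |
|---|---|
| Two-stage gate, by group | 38.6% |
| One-way ANOVA, always | 38.8% |
| Kruskal-Wallis, always | 35.4% |
| One-way ANOVA on logs | 44.5% |
| Arm F-test, raw scale, arm × duration model | 69.8% |
| Arm F-test, log scale, same model | 73.5% |

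A repeat gave 40% for the gate, 41% for ungated one-way ANOVA, 46% for its log version, and 69% and 73% for the two arm tests. A gate on pooled residuals gave 41%. With no treatment effect, the two-stage procedure rejected 4% to 5% of the time.

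The gate therefore costs about 0 points against the same ANOVA without it (38.8 − 38.6 = 0.2) and about 6 against the log version (44.5 − 38.6 = 5.9). Moving from the omnibus test to the arm test gains about 31 points on the raw scale (69.8 − 38.8 = 31.0).

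**The case against.** The strongest reply is that the plan never says the gate is run within groups. The 46%, 56% and 93% figures need by-group testing at 0.05 with an any-group-fails rule, and the 93% also needs independent outcomes, which is doubtful when all are measured in the same animals. With pooled residuals the gate separates normal from clearly skewed data reasonably well. A reader might infer that the choice of test is largely a matter of chance; the documents do not support that as a general statement. It holds for the by-group reading with normal or mildly skewed data. What remains is that the plan leaves the rule open.

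A reader might also infer that the dose-by-duration question is lost only when the rank test is chosen. That credits the ANOVA branch with a two-way model that the plan does not specify, and a one-way ANOVA over the groups loses the question too. Nor does Kruskal-Wallis leave the stated aim wholly unaddressed: it does test whether the groups differ, but cannot say whether dose, duration or both are responsible.

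Third, the gap from about 40% to about 70% power could be read as the price of the gate. It is not. Almost all of it comes from replacing a 12-group omnibus test with a focused 3-df arm test, which asks a different question. The example also uses multiplicative lognormal effects, which favours the log scale, and the plan offers no distributional data to support logging every outcome. These objections stand.

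**Conclusion.** The concern holds in a limited form. One Shapiro-Wilk result decides both summary and test for five outcomes, with its unit, level and decision rule unstated. If run by group at five animals and 0.05, with any failure triggering the rank test, it is close to uninformative. Even a single pooled-residual test would split five independent normal outcomes about one time in five. Separately, neither branch specifies an analysis of dose by duration, and dropping the gate alone would not supply one.

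Error control is not the problem: in the assumed example the two-stage type I error was 4% to 5%. The gate itself costs little power. The harm is that tests and summaries can differ between outcomes for no substantive reason, and that an unfocused omnibus comparison stands in for the factorial question. The size of that second loss, about 40% against about 70%, depends on the assumed effects and on arm effects that are constant over duration. All figures assume equal groups of five. This should be changed, but it does not by itself invalidate the study.

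**What to change.** Remove the normality gate and prespecify, for every numerical outcome:

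- one linear model with arm, duration and arm × duration;
- SH-0, which has no time-0 counterpart in the other arms, kept outside the factorial as a descriptive or separate comparison;
- estimated differences against KN with confidence intervals, or ratios where a log scale has been fixed in advance for that outcome;
- residual plots for description only, with no power to change the primary test;
- a permutation or rank-based sensitivity analysis, reported alongside the primary result and never replacing it.

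A blanket log transformation is not needed. If lesions regress to zero, an added constant could drive the result, so the scale deserves a decision outcome by outcome.

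The cost is a rewrite of the Data Analysis text: no new animals or measurements, and the model can be fitted in SPSS. The downside is that the analysis scale must be chosen for each outcome before the data are seen. The interaction will also be estimated imprecisely with five per cell, so its interval should be reported and a non-significant result should not be read as absence of interaction.

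### Only overall tests are planned and propolis is never named against the negative control, so a significant result cannot be attributed to propolis under any reading of the plan

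*Combined protocol and SAP*

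**What the plan says.** Study Planning describes the design: "The study involved 80 endometriosis mice which were randomly divided into 16 distinct groups". The groups are "the sham (SH) -0, SH-2, SH-4, SH-6, negative control (KN) -2, KN-4, KN groups -6" and "positive control (KP) -2, KP-4, KP-6, Dosage of Propolis 1 (P50) -2, P50-4, P50-6, Dosage Propolis 2 (P100) -2, P100-4, P100-6". Apart from sham, this is a complete 4 x 3 layout: KN, KP, P50 and P100, each at 2, 4 and 6 weeks. The section The Treatment lists one active agent besides propolis ("We use 0,1mg/Kg BW/day dienogest"). I take this to be the positive control, although the document does not say so.

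Data Analysis lists the numerical outcomes ("Data on lesion area of endometriosis tissue models, Bax / Bcl-2, Caspase 3, IL-1B, and PGE2 ratios") and plans Shapiro-Wilk to choose between the two tests in "Differences in endometriosis responses between dose and duration groups were performed with the Anova test (normal distribution) or Kruskal Wallis (abnormal distribution"). For the estrous cycle, "Changes in estrous cycles between groups are known through the chi square test". It says that averages or medians will be presented. No section names a contrast, a reference group, a follow-up test after a significant overall result, or an adjustment for several comparisons. Specimen Collection mentions one further comparison ("We take a picture of the lesion (to compare with the beginning lesion"), but this is within an animal and has no test attached.

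**The concern.** The title asks what propolis does to lesion growth and apoptosis. An overall test answers a different question: whether any group in it differs from any other. The design includes a positive control, which is normally there because it is expected to work. If it does work, the planned test can be significant when both propolis doses behave exactly like the negative control. The written plan then offers nothing further to separate the two explanations. The pairs, the adjustment and the time point would have to be chosen after the data are seen, across two doses, three durations and five numerical endpoints.

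The wording also leaves open which groups enter the test. It could be one-way over all groups, two-way arm by duration, arms within one duration, or only the six propolis groups, which are the only ones labelled by dosage in Study Planning. What a significant result means differs between these readings.

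**Working it through.** **Inputs from Study Planning.** Groups: sham 4 + KN 3 + KP 3 + P50 3 + P100 3 = 16, which agrees with the stated 16. Animals per group: 80 / 16 = 5 if allocation is equal, which is not stated. There is no sample size calculation to reproduce.

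**Assumed, because the plan is silent.** Alpha 0.05, normal data, SD 1 in every group, no losses, and effects of 1, 1.5 or 2 SD.

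**Check 1: only KP works, by d SD, and P50 = P100 = KN.** The arm means are (0, d, 0, 0), with sum of squares about their mean d² - d²/4 = 0.75d². Power comes from the noncentral F with noncentrality λ = (animals per mean) x (sum of squares).

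| Reading | λ | df | d = 1 | d = 1.5 | d = 2 |
|---|---|---|---|---|---|
| One-way, 12 groups | 5 x 3 x 0.75d² = 11.25d² | 11, 48 | 49% | 89% | 99.5% |
| Two-way, arm main effect | 15 x 0.75d² = 11.25d² | 3, 48 | 78% | 99% | 100% |
| Four arms, one duration | 5 x 0.75d² = 3.75d² | 3, 16 | 27% | 56% | 83% |

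Kruskal-Wallis, by simulation, gives 39 / 83 / 99% for 12 groups and 21 / 47 / 73% for four arms at one duration. If the four-arm test is run separately at each duration, the chance of at least one rejection is 1 - (1 - p)³. This is 61 / 92 / 99.5%, against 1 - 0.95³ = 14% with no effect anywhere.

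**Check 2: named contrasts in the same scenario.** P50 v KN and P100 v KN, averaged over duration, with Dunnett critical value 2.279 (two contrasts, correlation 0.5, 48 df). The simulated chance that either is significant is 4.9 to 5.2%, whatever KP does.

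**Check 3: the six propolis groups only.** KP is not in the data, so it cannot cause rejection. KN is not there either. A significant result says that the doses or durations differ from each other, not that either dose differs from no treatment.

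**Check 4: only time matters, s SD per step, same in every arm.** The duration means are (0, s, 2s), with sum of squares 2s².
- One-way, 12 groups: λ = 20 x 2s² = 40s², df 11, 48. Rejection is 43% at s = 0.5 and 99% at s = 1.
- Duration main effect of a two-way ANOVA: same λ, df 2, 48. Rejection is 79% and over 99.9%.
- One-way, six propolis groups: λ = 10 x 2s² = 20s², df 5, 24. Rejection is 29% and 89%.
- Arm main effect, or arms within one duration: the arm means are equal, so rejection stays at 5%.

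**Estrous cycle.** A chi-square between groups has the same gap: rejection does not say which group changed. The plan does not define the outcome categories, so I attach no percentage.

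**The case against.** The strongest reply is that this is a short plan, not a wrong one. ANOVA and Kruskal-Wallis are valid tests of the overall hypothesis, pairwise follow-up is customary, and the averages or medians to be presented would show a reader which arms moved. That is fair as far as it goes. The summaries reduce the risk of a plain misreading, and nothing here says that the overall test is invalid. But no follow-up is written, and group summaries without a named comparison do not supply the missing inference.

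A second reply is that the positive-control mechanism depends on KP being in the test. That stands. A reader might infer that an effective positive control can produce significance under any reading of the plan. The document does not support this: the sentence can be read as covering only the six propolis groups, where KP plays no part. The fault is then that no control is tested at all.

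A reader might also infer that time alone can mislead only in the one-way test. That is not so either, because the duration effect of a two-way ANOVA rejects too. Only the arm tests are protected.

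Nor is there a claim here that choosing the test by Shapiro-Wilk inflates type I error, or that the overall tests lack power. If all three active arms shift by 1 SD, the arm main effect has 78% power, against 68% for one averaged Dunnett contrast.

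Sham could be a further source of rejection if included. However, the document does not define sham, and equal-SD lesion data may not apply to it, so no figure is relied on.

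**Conclusion.** The point holds in conditional form. The plan names only overall tests, and no section names propolis against KN. Under every available reading, a significant result from the stated tests does not show that propolis differs from KN. Where KP is included, its effect alone gives rejection rates from 27% (1 SD, four arms at one duration) to practically 100% (2 SD, one-way or arm main effect). Where only the propolis groups are included, there is no control comparison to be significant.

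The percentages rest on 5 animals per group, alpha 0.05, normal data, equal SD and assumed effect sizes, and serve only as illustration. The logical gap needs none of them. It also does not need KP to be dienogest, only to be an effective control. The randomised data remain usable, so this should be corrected in the plan; it does not undermine the study.

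**What to change.** For lesion area and each marker, fit one model with arm (KN, KP, P50, P100) by duration (2, 4, 6 weeks). Then:
- Name P50 v KN and P100 v KN, averaged over duration and Dunnett-adjusted, as the main comparisons.
- Report the arm-by-duration test and the per-duration estimates with confidence intervals.
- Report P100 v P50 as the secondary dose comparison, and KP v KN as a check that the model responds.
- Keep sham out of these contrasts.
- If ranks are used, make the same two comparisons by rank-sum tests stratified by duration, with Holm adjustment.
- For the estrous cycle, use exact P50 v KN and P100 v KN tests stratified by duration, with Holm adjustment, once the outcome categories are stated.

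This changes analysis wording only; animals, procedures and treatments stay as they are. It has three statistical costs:
- **Averaging dilutes a late-only effect.** If propolis acts only at 6 weeks by 1.5 / 2 SD, the averaged contrast has noncentrality (d/3) x √(15/2) = 1.37 / 1.83 and power 19 / 33%. A 6-week contrast has d x √(5/2) = 2.37 / 3.16 and power 54 / 81%. The per-duration estimates partly offset this. If the effect is constant over time at 1 / 1.5 SD, the order reverses: 68 / 96% averaged, 25 / 54% at 6 weeks.
- **Dunnett does not control error across the five endpoints.** Five families at 5% give 1 - 0.95⁵ = 23% if independent, and about 14% at correlation 0.8.
- **The stratified rank comparison is slightly weaker:** 63% power at 1 SD, against 68%. The power of the stratified exact estrous test was not calculated.
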